5.4.2 Part II (Patients with HER2+ breast cancer)

Inclusion Criteria:

Patients will only be included in the study if they meet all of the following criteria:

- Patients who have given informed consent
- Patients that agree not to drink alcoholic beverages or use any drugs during the study
- Age: at least 18 years old
- Patients with local, locally advanced or metastatic HER2+ breast carcinoma as diagnosed on biopsied tissue by immunohistochemistry or fluorescence in situ hybridization (FISH).

Exclusion Criteria

Patients will not be included in the study if one of the following criteria applies:

- Pregnant patients
- Breast feeding patients
- Patients with occupational exposure to ionizing irradiation
- Patients with active thyroid dysfunction (abnormal TSH value)
- Patients that received radiolabeled compounds with a long half-life (>7h) for diagnostic or therapeutic purposes within the last 2 days.
- Patients with absolute contra-indications for thyroid blockage with potassium iodide.
- Patients with abnormal liver: ALT/AST > 2 times normal values; bilirubin > 1.5 time normal values.
- Patients with abnormal kidney function: < 50 ml/min/1,73 m²
- Patients with recent (< 1 week) gastrointestinal disorders (CTCAE v4.0 grade 3 or 4) with diarrhea as major symptom
- Patients with any serious active infection
- Patients who have any other life-threatening illness or organ system dysfunction, which in the opinion of the investigator would either compromise patient safety or interfere with the evaluation of the safety of the test radiopharmaceutical
- Patients who cannot communicate reliably with the investigator

CAMEL-IDS NV [name]	Page 18 of 36
www.camel-ids.com	

- Patients who are unlikely to cooperate with the requirements of the study
- Patients at increased risk of death from a pre-existing concurrent illness
- Patients who participated already in this study
- Patients who participated in a previous trial with Anti-HER2 VHH1

Withdrawal of patients

The patient may withdraw from the study at any time without giving reasons and without any disadvantageous consequences for his/her subsequent medical care.

The investigator may withdraw a patient from the study at any time in case of intercurrent illness, AE, therapeutic procedure or as a general rule if further participation in the study is believed to be to the patient's detriment.

Any patient withdrawn from the study before the scheduled completion of the study procedures will be considered an early withdrawal, regardless of the reason for withdrawal. For safety reasons, reasonable attempt should be made to contact withdrawn subjects 24h after the administration of the investigational product to gather information on AEs. For his/her own safety, subjects will be reminded to continue potassium iodide ingestion until $48\pm12h$ after administration of [¹³¹I]-SGMIB Anti-HER2 VHH1. Information collected as a result should be recorded on the appropriate CRF pages.

Patients withdrawn from the study will be replaced.

Patient recruitment

Patients with HER2+ breast cancer will be recruited by the PI at UZ Brussel and possibly via the ClinicoBru patient recruitment network.

5.5 Clinical Laboratories, Technical Department(s), Institution(s) Providing Clinical Study Services

The local department of clinical chemistry and hematology will perform the clinical laboratory testing of blood samples.

The local nuclear medicine department will provide the analyses of the blood and urine samples:

Whole blood and plasma samples will be counted against appropriate standards of known dilution in an automatic gamma well counter and, after correction for decay and background activity, expressed as a percentage of the injected activity (%IA). The blood volume of each volunteer will be estimated according to body weight and height, using Nadler's formula and the subject's hematocrit

Plasma and urine aliquots will be analyzed by size-exclusion chromatography (SEC) or reverse-

phase high pressure liquid chromatography (RP-HPLC) to identify possible metabolites.

The PI of the local nuclear medicine department will also perform the analyses of the dynamic planar scan, the total body scans and the SPECT/CT scans.

From the dynamic planar scan, time activity curves for kidney and liver activity will be drawn. The total body scans will be used for region of interest analysis to derive input data for the OLINDA/EXM software 1.0 in order to calculate dosimetry data (12).

SPECT/CT scans will be analyzed visually and tumor uptake will be scored by the PI: intense, moderate, low or no uptake. In addition, tumor lesions will be quantified to obtain a measurement of activity per unit of volume.

5.6 Image acquisition parameters

The subject will be scanned feet first in supine position.

	Collimator	r scan kidneys&liver (gamma camera): HEGP	
	Zoom	1 (Full field)	
	Matrix	256 x 256	
	Energy Window	20% (6% low, 6% high scatter window)	
	Frames/duration	30 frames of 60s	
•	I-131 Total body plan	nar scan:	
	Collimator	HEGP	
	Zoom	1.11 (Full field)	
	Matrix	High-resolution (1024 x 512)	
	Energy Window	20% (6% low, 6% high scatter window)	
	Scan speed	10 cm/min	
•	1	n of 1 region with a cancer lesion:	
	Collimator	HEGP	
	Matrix	128 x 128	
	Energy Window	20% (6% low, 6% high scatter window)	
	Rotation	360	
	Total projection	64	
	Time/projection	30s	
•	Surview CT acquisit	ion:	
	Voltage	120 kV, 30 mA	
	Rotation	180	
	Rotation time	24s	
	Exposure	580 mAs	
	Matrix	512 x 512	
	Pixel size	1,667 mm	
	CAMEL-IDS NV		

CAMEL-IDS NV
[name]
www.camel-ids.com

[figure not shown]
Slice thickness	1 mm
Segments	3
CDTDI (mGy)	15

5.7 Investigational product

Composition:

The colorless, clear, sterile solution contains the radioactive [¹³¹I]-SGMIB Anti-HER2 VHH1 in Phosphate Buffered Saline (PBS).

¹³¹I radiolabeled N-succinimidyl 4-guanidinomethyl-3-iodobenzoate (SGMIB) conjugated anti-HER2 VHH1 protein referred to as [¹³¹I]-anti-HER2 VHH1:

Route of administration:

IV-injection of [¹³¹I]-SGMIB Anti-HER2 VHH1 using an infusion pump within 5±3min via an intravenous line inserted in a vein or port-a-cath

Dosage regimen: A continuous infusion of 50±40µg with radioactivity of 64±46MBq

Treatment period:

The product will be administered as a single dose with a radioactivity of 46±28MBq for healthy volunteers.

CAMEL-IDS NV [name]	Page 21 of 36
www.camel-ids.com	

In HER2+ breast cancer patients the product will be administered as a single dose with a radioactivity of $64\pm46MBq$.

Labeling information:

Primary label example:

[¹³¹I]-SGMIB Anti-HER2 VHH1 Lot number: **151109154TEST** Study code: CAM-VHH1 For clinical trial use only For intravenous administration Caution: Radioactive material Principal investigator: [name] Details: See outer packaging

Secondary label example:

			ANTI-HERZ VHH1			
	s	solution for in	Anti-HER2 VHH1 travenous injection			
	lot number	·····		- · · ·		
9A)		data	00 11 2015			
1911	manufacturing	date				
				9		
				1.1		
ć.,				1		
			Protocol CAM-VHH1			
	principal invest For intravenous administ	igator	[name]	· · ·		
	For clinical trial use only					
	Storage at room tempe					
	manufacturer					
	VUmc (lversity al Croter				~
			the second			
	VU University Medical Cent Radiology and Nuclear Med	ter dicine	ALK AN			
	Radionuclide center				 1 3 	
	[name]	lead to ntain	turing a second	J		
		,				
			Consignee:			
			[name] ([name])		
			Universitair Ziekerhuis Brussel	·		
			Nucleaire geneeskunde	1		
			[name]	1		
			[name]			
			Consignee:	 		
			Consignee: [name] ([name] Universitair Zlekerhuis Brussel Nucleaire geneeskunde [name])))		
			[name] ([name] Universitair Ziekerhuis Brussel Nucleaire geneeskunde)))) ()) () () () () () (
			[name] ([name] Universitair Ziekerhuis Brussel Nucleaire geneeskunde [name])))		
			[name] ([name] Universitair Ziekerhuis Brussel Nucleaire geneeskunde [name]			

The product will be received by the radiopharmacist of UZ Brussel, checked for its integrity and recorded on the Drug Receipt Form. The radiopharmacist will be responsible for receiving the batch release certificate and the QC results of the received batch from the manufacturer. The radiopharmacist will contact the QP of the manufacturer to have the authorization of use. The product will be stored at 5 ± 3 °C until use. The product will normally be used within 24h after production by the manufacturer. The radiopharmacist of UZ Brussel could ask the QP of the manufacturer for authorization to use the product at a later time point based on stability data. The product will be drawn into a 20ml syringe and a 0.9% NaCl solution for injection will be added to obtain a final volume of 15ml. The injection syringe will need to be labeled with the appropriate identification label. The product will only be administered in the presence of a physician.

The radiopharmacy and the investigators will keep adequate records for the receipt, preparation, administration and return of study medication. They would not allow the study medication to be used for purposes other than as directed by this protocol. All data regarding the study medication must be recorded in the relevant forms provided by the Sponsor.

The radiopharmacy will allow the used study drug (empty vials) to decay and be destroyed according to the local procedures for destruction of radioactive waste.

In case of remaining treatment (vials not used), these will have to be destroyed according to the local procedures for destruction of radioactive waste.

5.8 Previous and concomitant medication/therapy

The subject should not have received radiolabeled compounds with a long half-life (>7h) for diagnostic or therapeutic purposes within the last 2 days.

Other medication to treat AEs might only be prescribed after consultation of the PI, unless in case of an emergency situation.

5.8.1 Potential risks and benefits to human subjects

Potential Risks

All medicinal products can have known or unforeseeable side effects. The previous study UZBRU-VHH1 has shown that a similar product was well-tolerated, without any side effects. However unknown side effects or discomforts could appear.

The administration of the product in a vein and blood sampling (around 5ml of blood) might (rarely) cause pain, bleeding, bruising or infection localised around the injection site. Similarly, some subjects might feel dizzy or even faint during the procedure. The clinical team that will perform this procedure will do all they can to keep these discomforts to a minimum.

During this investigation the subjects will be exposed to a low amount of ionizing radiation. The past study involving a similar product showed that the exposure to radiation was very low, and lower that the exposure caused by a routinely performed FDG-PET scan.

No information is available that can predict an interaction with the current product. Preclinical studies showed no interactions with anti-HER2 treatments such as PertuzumAb and TrastuzumAb (7).

Benefits

For the healthy volunteers, no benefits are expected.

For the HER2+ breast cancer patients the investigated diagnostic product might or might not prove beneficial in diagnosing and treatment of the disease.

The information obtained thanks to this study might contribute to a better knowledge of the use of this investigational product or to the development of a new medicinal product for the diagnosis and treatment of breast cancer in patients.

5.9 Outcome measures of safety, tolerability and tumor targeting

5.9.1 Primary outcome measures of safety and tolerability

Tolerability and safety of [¹³¹I]-SGMIB Anti-HER2 VHH1 will be assessed by the collection and evaluation of data pertaining to all AEs experienced by subjects during the study. Subjects will undergo a physical examination including vital signs and be asked about changes in concomitant diseases and general physical and emotional state using open, non-leading questions. Blood will be collected for hematology and clinical chemistry.

A physical examination including vital signs (arterial blood pressure and pulse rate) will be performed pre-administration. Additionally the vital signs will be monitored at 5 ± 10 min post-administration. A second physical exam will be performed at 4.5 ± 1 h post-administration for the healthy subjects and at 3 ± 1 h for the HER2+ breast cancer patients.

Safety laboratory examination: A blood sampling will be performed before and at 24 \pm 4h after the administration of the [¹³¹I]-SGMIB Anti-HER2 VHH1, using 1 lithium/heparin sample of 5ml and 1 EDTA sample of 2.6ml at each time point.

Any clinically relevant change from a baseline laboratory value will be recorded as an AE in the CRF unless it can reasonably be assumed to result from improper handling, a measurement error or some other technical cause.

From the hematology and clinical chemistry we expect no major changes ($\pm 20\%$ deviation of the baseline value and outside of the laboratory reference values).

We expect no significant changes in the physical exam in comparison with the physical exam before product administration.

From the blood sampling we expect to obtain the time-activity curve of the product in blood to be biphasic with a rapid distribution and elimination phase. After 24h we expect that less than 10% IA will be present in the blood.

From the urine sampling we will measure the fraction of un-metabolized product.

Human biodistribution will be assessed for the healthy volunteers using the dynamic scan and planar total body scans.

From the imaging results we expect to visualize liver and kidney as primary elimination routes and potentially uptake in tissues with physiological HER2 expression such as thyroid, pituitary, salivary, lacrimal, sweat glands and intestines.

Human dosimetry will be quantified using region of interest measurements on the total body scan of the different subjects. OLINDA/EXM software 1.0 will be used to generate dosimetry estimates for the healthy subjects (12).

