5.11.3 Biodistribution and dosimetry

For the biodistribution evaluation, all organs with an uptake higher than the background (surrounding soft tissues) will be included in the evaluation as source organs.

The percentage of injected activity (%IA) will be calculated, in each set of images, as the ratio between the measured activity in the organ and the injected activity. Organ time activity curves

will be generated, plotting %IA vs. time. The individual and mean blood and plasma timeactivity curves will be obtained using the measured activity in blood and plasma samples.

All dosimetric evaluations will be done using the OLINDA/EXM 1.0 software (12). Total dose estimates and the dose estimate for the organs with the highest dose (most likely kidney and bladder) will be reported using classical descriptive statistics for continuous variables (N, n, mean, median, standard deviation, minimum and maximum).

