5.13 Overview of investigational actions

Table 1. Overview of the investigational actions that need to be performed at different visit times for each subject in part I of the study. V1: Visit 1; V2: Visit 2; V3: Visit 3; V4: Visit 4; V5: Visit 5

		V1	V2		V3					V4		V5								
Action	Total			pre	0min	5min	10min	20min	30min	40min	60min	105min	120min	225min	240min	4.5h	23.75h	24h	71.75h	72h
Informed consent	1	х																		
Inclusion/exclusion criteria	1	x																		
Medical history	1	х																		
Subject information: fasting&thyroid blocking drugs	2	х	х																	
Delivery thyroid blocking drugs	4		х	х													2x			
Confirmation of ingestion thyroid blocking drugs	4		х	х													х		х	
Blood sample for HCG test	1		х																	
Physical exam	2			х												х				
Vital signs	3			х		x										х				
Blood sample lithium heparine	13		х	2x		х	х	х	х		х	х		х			2x		х	
Blood sample EDTA	3		х	х													х			
Urine sampling	4										х			х			х		х	
Intravenous line&saline infusion	1			х																
Administration [¹³¹ I]-Anti-HER2 VHH1	1				х															
Measurement of residual activity in syringe and line	1				х															
If subject cannot withhold: urine collection&scan TB1	1									х										
Dynamic renal scan (30 min)	1				х															
Total body (TB) planar scan	5									х			х		х			х		x
Counting blood/plasma (radioactivity)	10			х		х	х	х	х		х	х		х			х		х	
HPLC analysis (metabolites in blood)	5						х				х			х			х		х	
HPLC analysis (metabolites in urine)	4										х			х			х		х	
Clinical chemistry/Hematology analysis	3		х	х													х			
HCG test	1		х																	
Dosimetry analysis Total body planar scans	5									х			х		х			х		х

CAMEL-IDS NV [name]	Page 29 of 36
www.camel-ids.com	

Table 2. Overview of the investigational actions that need to be performed at different visit times for each patient in part II of the study. V1: Visit 1; V2: Visit 2; V3: Visit 3; V4: Visit 4

		V1	/1 V2 V3								V4				
Action	Total			pre	0min	5min	15min	60min	120min	2.5h	3h	23.75h	24h	24.5h	
Informed consent	1	х													
Inclusion/exclusion criteria	1	х													
Medical history	1	х													
Patient information: fasting& thyroid blocking drugs	2	х	x												
Delivery thyroid blocking drugs	4		x	x								2x			
Confirmation of ingestion thyroid blocking drugs	3		x	x								x			
Blood sample for HCG test	1		x												
Physical exam	2			x							х				

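### The blood curve described as that of the product is a total-radioactivity curve, and the five plasma HPLC runs that could show intact product have no planned use in it

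*Combined protocol and SAP*

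**What the plan says.** Section 5.9.1, under the primary outcome measures, states the expectation for the blood data: "we expect to obtain the time-activity curve of the product in blood to be biphasic", with a rapid distribution and elimination phase. It adds that less than 10% of the injected activity (IA) should be in the blood after 24 h.

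Two other sections say how the curve is made. Section 5.5 has whole blood and plasma counted in a gamma well counter and, "after correction for decay and background activity, expressed as a percentage of the injected activity (%IA"). Section 5.11.3 says: "The individual and mean blood and plasma timeactivity curves will be obtained using the measured activity in blood and plasma samples".

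Chromatography of plasma and urine is described in section 5.5 as size-exclusion or reverse-"phase high pressure liquid chromatography (RP-HPLC) to identify possible metabolites". Only for urine does the plan go further: "From the urine sampling we will measure the fraction of un-metabolized product" (section 5.9.1). Section 5.11 gives no summary or analysis of the plasma HPLC results.

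**The concern.** A gamma counter registers iodine-131 whatever molecule carries it. Intact compound, a labelled fragment and free iodide all add to the same count. The curve in section 5.11.3 therefore equals the curve of the product only if everything labelled in plasma is intact.

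This is a first-in-man study of a compound intended for targeted radionuclide therapy, and biodistribution is a primary objective of Part I. How fast the intact targeting agent leaves the blood is one of the things a reader will want from these six volunteers. If the total-activity curve is described as the product's, its level may be too high and its late phase too flat. The reader could not tell, because the measurement that would settle it is collected but not tied to the curve.

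**Working it through.** **The schedule.** Table 1 (section 5.13) gives totals of 10 for blood and plasma counting and 5 for HPLC of metabolites in blood. Both totals are reproduced from its columns:

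- Counting: pre-dose, 5, 10, 20, 30, 60, 105 and 225 min, 23.75 h, 71.75 h, which makes 10.
- Plasma HPLC: 10, 60 and 225 min, 23.75 h, 71.75 h, which makes 5.

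All five HPLC times are also counting times, and the visit text in section 5.3.1 names both purposes for each of those draws. At 23.75 h the visit text omits the plasma filtration and injection step, although the item's own title and Table 1 both include the metabolite analysis. Over six volunteers this makes 6 × 5 = 30 paired results. Part II has one post-dose activity sample, at 60 min, with HPLC (Table 2), so it yields no curve.

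**Effect on level.** Let A(t) be total plasma activity in %IA and f(t) the intact fraction. Intact product is f(t) × A(t), so total activity overstates it by 1/f(t):

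- f = 1: no bias
- f = 0.8: 1/0.8 = 1.25-fold
- f = 0.5: 1/0.5 = 2-fold

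**Effect on the apparent rate of decline.** Between 225 min (3.75 h) and 23.75 h there are 20 h. A two-point half-life is ln 2 × 20 / ln(ratio of the earlier value to the later one). The documents give neither A(t) nor f(t), so every value below is an assumption.

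| Total activity, %IA | f at 225 min → 23.75 h | Half-life, total | Half-life, intact | Total / intact |
|---|---|---|---|---|
| 10 → 5 | 1 → 1 | 20.0 h | 20.0 h | 1.00 |
| 10 → 5 | 0.90 → 0.90 | 20.0 h | 20.0 h | 1.00 |
| 10 → 5 | 0.95 → 0.80 | 20.0 h | 16.0 h | 1.25 |
| 10 → 5 | 0.90 → 0.50 | 20.0 h | 10.8 h | 1.85 |
| 10 → 1 | 0.95 → 0.80 | 6.0 h | 5.6 h | 1.07 |
| 10 → 1 | 0.90 → 0.50 | 6.0 h | 4.8 h | 1.26 |

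For the fourth row, intact product falls from 10 × 0.90 = 9.0 to 5 × 0.50 = 2.5 %IA, a ratio of 3.6, and ln 2 × 20 / ln 3.6 = 10.8 h.

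A constant fraction below 1 biases the level but not the slope. A falling fraction makes elimination look slower, and less so when total activity itself falls fast. A rising fraction would act the other way: with 10 → 5 %IA and f going from 0.5 to 0.8, the intact half-life would be 62.1 h against 20.0 h for total activity.

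**The case against.** The strongest reply is that little depends on this curve, and most of that reply stands.

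- **Half-life.** A reader might infer that the plan will report an overstated elimination half-life for the product. It will not. Section 5.11.3 plans individual and mean curves, with no fit and no elimination parameter. Section 5.9.1 offers only a qualitative expectation about phases.
- **Metabolites as a fact.** A reader might also infer that metabolites do circulate and dominate late. The documents speak only of possible metabolites and give no plasma data, so any overstatement is conditional.
- **The 24 h expectation.** It is worded as injected activity, so total counts are the right measure. Intact product cannot exceed total activity, so a total below 10% IA also bounds the product.
- **Dosimetry and the DSMB.** Total activity is the appropriate quantity for radiation dose, and the dosimetry input comes from regions of interest on the total body scans. The DSMB decision rests on the safety profile (section 5.12).
- **Section 5.11.3 itself.** It speaks of time-activity curves from measured activity. The wrong label sits in section 5.9.1.
- **Nothing is lost.** The paired samples exist, so intact fractions could be worked out later.

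The last point stands only in part. If the calculation is left until afterwards, the rules for weak chromatograms and for interpolation are chosen with the data in view. Meanwhile section 5.9.1 already invites the report to read the total-activity curve as the product's elimination.

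The correction also has limits. HPLC is run on plasma, so it does not carry over directly to whole blood. There is no HPLC between 225 min, 23.75 h and 71.75 h, and late runs may hold too little activity to evaluate.

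**Conclusion.** The concern holds as a mismatch between what section 5.9.1 says the curve describes and what sections 5.5 and 5.11.3 compute. Not knowing the intact fraction does not excuse leaving it out. It is the reason to use the five scheduled HPLC runs that could measure it.

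The size cannot be stated from the documents. The level is overstated only if labelled metabolites circulate. The product's elimination phase looks slower only if the intact fraction falls with time; in the falling-fraction scenarios tabulated above, the two-point half-life is 1.07 to 1.85 times too long, and that range reflects assumed inputs. The documents do not support any claim that a planned half-life, the 24 h expectation, the dosimetry or the decision to open Part II is wrong. This is a worthwhile, inexpensive improvement to the interpretation of Part I, not the repair of a failed endpoint.

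**What to change.** For Part I, in sections 5.9.1 and 5.11.3:

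1. Label the existing blood and plasma curves 'total radioactivity' and keep them.
2. Quantify the intact fraction in each of the five scheduled plasma HPLC runs, and bring the 23.75 h visit text into line with Table 1.
3. Report intact product (plasma %IA × intact fraction) for each volunteer at those five times, beside total activity.
4. If a continuous intact-product plasma curve is drawn, state the interpolation rule in advance and mark the curve as uncertain between 225 min, 23.75 h and 71.75 h.
5. Report HPLC runs with too little activity as not evaluable, by a rule fixed beforehand.
6. Describe the product's distribution and elimination from this plasma curve. State that the correction does not apply directly to whole blood.

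For Part II, report the 60 min intact fraction beside the single activity measurement.

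The cost is protocol wording and a small calculation on chromatograms already scheduled, with no new draw, visit or assay. The drawback is that the late fractions will be imprecise and some may be missing.
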